This study is a preliminary randomized control trial evaluating a 9-week diet and lifestyle intervention on quality of life, patient-reported symptoms, and biomarkers associated with methylation. We will recruit forty-eight participants with 24 randomized to each study group. Refer to Figure 1 for an overview of the study flow.

Figure 1. Study Flow Overview

D.2 Study Intervention

Study participants will be randomized into an intervention or control group. The intervention group will undergo a 3-week washout period following the discontinuation of any non-medically required nutrition or herbal supplements. The intervention group will follow detailed diet and lifestyle recommendations over a 9-week period. Two webinars at the start of the

Protocol

Study Title: Methylation Diet and Lifestyle (MDL) Study

PI: [name], ND, MPH and [name], ND

IRB #: RB100217

Approval Date: 2.9.18

Ver. 1.1

intervention phase will provide information to participants on proper food and exercise choices, as well as how to access and use the required electronic resources (apps).

The control group will undergo the same testing measures as the intervention group, but will not have access to the education information or be instructed to change diet or lifestyle factors. They will have access to the information after the study is complete.

D.2.1 Diet Recommendations

Specific dietary guidelines will be outlined for participants and should include the following:

Per week	Per day

3 servings of liver
 
 • (1 serving = 3 oz) • Choose preferably organic liver 
5-10 eggs
 
 • Ideally free-range, organic, omega-3 enriched 	
2 cups of dark leafy greens
 
 • Measured raw, chopped, and packed • Including kale, Swiss chard, collards, spinach, dandelion, mustard greens • Does not include salad greens such as romaine, iceberg, Spring mix 
2 cups cruciferous vegetables
 
 • Measured raw, chopped, and packed • Including broccoli, cabbage, cauliflower, Brussels sprouts, bok choy, arugula, kale, watercress, rutabaga, kohlrabi, radish, turnip
General	

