Not all foods recommended and consumed during the study intervention may be captured by VioScreen. An additional food frequency questionnaire (FFQ), with approximately 250 foods and beverages, was created to assess consumption. It has been designed to be consistent with the validated block Brief FFQ by NutritionQuest. This will be administered electronically via RedCap online database to all study participants at Visits 1, 2, and 3.

D.2.7.5. Adherence phone calls

Participants will be contacted via phone once per week during the first 4 weeks of the study and every other week for the remainder of the study. Designated health coaches will assess for adherence to the study intervention including dietary, stress management, and exercise recommendations. Participants will be able to ask questions pertaining to the study intervention.

Refer to Appendix B for detailed script of these phone calls.

Protocol

Study Title: Methylation Diet and Lifestyle (MDL) Study

PI: [name], ND, MPH and [name], ND

IRB #: RB100217

Approval Date: 2.9.18

Ver. 1.1

D.3 Description of Participant Population

D.3.1. Participant Characteristics

Sample size: n=48

We will enroll and randomize up to 48 people which will allow for 20% attrition such that we have an evaluated sample size of 40 to allow for withdraws or dropouts.

Age: 50-72

Gender: Males only

Minorities: all racial and ethnic backgrounds will be recruited from the general population without preference or discrimination.

Vulnerable Populations (e.g. children, pregnant women, cognitively impaired): No vulnerable populations will be enrolled.

D.3.2. Inclusion and Exclusion Criteria

Individuals must meet the following participation criteria:

Inclusion criteria:

- Males, ages 50-72
- Willing to adhere to 9 weeks of a dietary and lifestyle program including specific nutrition and exercise guidelines
- Willing to avoid any over-the-counter medications, supplements or herbal products for the length of the study, except short-term use (<1 week) use at least 1 week before scheduled study visits
- Willing to have blood drawn three times and abstain from food or beverage intake for 10-12 hours before blood draws
- Willing to provide saliva samples
- Willing to track food intake, sleep, stress management techniques, and exercise daily
- Willing to drink a nutrient-enriched beverage and take a encapsulated probiotic daily
- Willing and able to use electronic devices and connect to the internet

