The following procedures, evaluation and/or assessments will be obtained at Study Visit 2:

- Weight
- Vital signs including heart rate, blood pressure, respiration rate and temperature
- Questionnaires including Lifestyle Habits, PROMIS-29, MYMOP, MSQ, and NUNM Adverse Events, VioScreen
- Blood draw to collect 2 tubes of blood
- Saliva sample
- If in intervention group, will receive study supplements for remaining 4 weeks of study
- Case report form completed by study staff

Study Visit 3 (Week 9)

The following procedures, evaluation and/or assessments will be obtained at Study Visit 3:

- Weight
- Waist-to-hip ratio will be calculated as previous defined in Study Visit 1
- Vital signs including heart rate, blood pressure, respiration rate and temperature.
- Questionnaires including Lifestyle Habits, PROMIS-29, MYMOP, MSQ, and NUNM Adverse Events, VioScreen
- Blood draw to collect 2 tubes of blood
- Saliva sample
- If in intervention group, return unused supplements
- Case report form completed by study staff

Protocol

Study Title: Methylation Diet and Lifestyle (MDL) Study

PI: [name], ND, MPH and [name], ND

IRB #: RB100217

Approval Date: 2.9.18

Ver. 1.1

D.5.9. Educational Webinars

Weekly, live webinars will provide information on the diet, exercise, stress management, and lifestyle recommendations. Prior to initiating any of these changes, an introductory webinar will provide an overview of the study intervention. An additional webinar will provide detailed instruction on how to access and utilize two electronic applications – MBody360 and Stress Free Now. All webinars will be delivered via Zoom, a free online communication application.

Refer to Appendix C for detailed information on webinar content

D.6. Study Withdrawal and/or Early Termination

Participants will be informed that they have the right to withdraw from the study at any time, without affecting their relationship with NUNM. Participants may also be discontinued from the study if the investigators determine it is in the best interest of the participant.

Information about study withdrawal or premature discontinuation from the study will be captured throughout the study. Study withdrawal or premature discontinuation will be categorized as follows:

- Participant began taking an excluded medication or supplement

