- The Principal/Clinical Investigator decided that withdrawal/discontinuation was in the best interest of the participant due to an adverse event, non-compliance, or another reason
- The participant requests withdrawal from the study for reasons other than above
- The participant failed to return for study visits

If a participant withdraws before the second visit, they will be replaced, however participants who withdraw between the second and third visits will not be replaced. Every effort will be made to collect a final salivary sample and all final labs from all participants, even if they withdraw from the study early.

D.7. Study Products

D.7.1. PhytoGanix (tropical fruit flavor)

Organic Superfruits & Greens Powder Drink Mix is a food-based phytonutrient blend designed to support intestinal health and immune function.

Protocol

Study Title: Methylation Diet and Lifestyle (MDL) Study

PI: [name], ND, MPH and [name], ND

IRB #: RB100217

Approval Date: 2.9.18

Ver. 1.1

Serving Size: 1 Scoop (10.4 grams)

Ingredient	Amount per serving
Calories	40
Total Carbohydrate	9 g
Dietary Fiber	1 g
Sugars	1 g
Protein	1 g
Vitamin C (as ascorbic acid)	100 mg
Calcium	20 mg
Iron	1.4 mg
Sodium	30 mg
Organic Seed and Prebiotic Blend:	5.53 g
Isomalto-Oligosaccharide, Flax Seed Powder, Chia Seed Powder, Quinoa (Chenopodium quinoa Willd.) Sprout Powder	
Organic Veggie Blend:	2.35 g
Spirulina Whole Algae Powder, Carrot Root Powder, Broccoli Head Powder, Cauliflower Head Powder, Spinach Leaf Powder, Parsley Leaf Powder, Bamboo Shoot Extract, Beet Root Powder	
Organic Fruit Blend:	1.2 g
Apple Fruit Powder, Pineapple Fruit Powder, Strawberry Fruit Powder, Raspberry Fruit Powder, Blackberry Fruit Powder, Blueberry Fruit Powder	
Herbal Support Blend:	300 mg
Milk Thistle Seed Extract, Turmeric Rhizome Extract, Green Tea Leaf Extract, Reishi Mushroom Whole Plant Powder, Maitake Mushroom Whole Plant Powder, Shiitake Mushroom Whole Plant Powder, Japanese Knotweed Root Extract, Quercetin Dihydrate, Organic Maca Root Powder, Organic Cassia Bark Powder, Dong Quai Root Powder, Ginger Root Powder, Garlic Bulb Powder	
Enzyme Blend (including protease, amylase, lipase, and cellulase)	200 mg
Lactobacillus acidophilus VK3 Strain	200 mg

Protocol

Study Title: Methylation Diet and Lifestyle (MDL) Study

PI: [name], ND, MPH and [name], ND

IRB #: RB100217

Approval Date: 2.9.18

Ver. 1.1

D.7.2. UltraFlora Intensive Care

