Serious Adverse Event (SAE): Any untoward medical occurrence that results in death, is life-threatening, requires inpatient hospitalization or prolongation of existing hospitalization, results in persistent or significant disability or incapacity, or results in a congenital anomaly or birth defect. Other important medical events requiring medical or surgical intervention to prevent a serious outcome would also be considered SAEs.

Unanticipated Problems (UP): Any incident, experience, or outcome that meets all of the following criteria: 1) unexpected (in terms of nature, severity, or frequency) given (a) the research procedures that are described in the protocol-related documents, such as the IRB-approved research protocol and informed consent document; and (b) the characteristics of the subject population being studied; 2) related or possibly related to participation in the research and 3) suggests that the research places subjects or others at a greater risk of harm (including physical, psychological, economic, or social harm) than was previously known or recognized.

G.4. Statistical Analysis

PROMIS 29 T-scores will be presented as mean (SD), for each group at each of the three data collection time points. For the primary aim, we will compare changes in PROMIS-29 T-scores between groups, using a linear mixed model with random intercept to test for a Group*Visit interaction. If there is a significant main effect, we will also present uncorrected contrasts comparing changes from baseline to Week 5, and from baseline to Week 9, between groups.

Although PROMIS T-scores are not particularly susceptible to extreme outliers, data will be examined for any outlying PROMIS scores or changes in PROMIS scores. If these scores are deemed to be in error, then they will be treated as missing in all analyses. Otherwise, scores

Protocol

Study Title: Methylation Diet and Lifestyle (MDL) Study

PI: [name], ND, MPH and [name], ND

IRB #: RB100217

Approval Date: 2.9.18

Ver. 1.1

will be retained in the main analysis; but we will conduct separate sensitivity analyses to test for effects of outlying data on results.

Mixed models incorporate all available data, without excluding any participants from analysis. Nevertheless, any participants who have baseline data only will be excluded from analysis. As an exploratory follow-up analysis, we will re-analyze changes from Week 1 to Week 9, using data from completers only.

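### After early withdrawal the protocol does not name PROMIS-29 for collection, so withdrawals for non-compliance, which fall mainly on the intervention arm, can selectively remove poor adherers from the primary comparison

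*Protocol*

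**What the plan says.** Section D.6 of the protocol provides for men to be discontinued from the study and lists categories for recording why. One category is an investigator's decision, made in the participant's best interest, "due to an adverse event, non-compliance, or another reason". Two other categories stand apart from it: "Participant began taking an excluded medication or supplement" and "The participant failed to return for study visits".

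On data after withdrawal, D.6 says: "Every effort will be made to collect a final salivary sample and all final labs from all participants, even if they withdraw" early. Questionnaires are not mentioned there. D.6 also has men who withdraw before Visit 2 replaced, but not those who withdraw between Visits 2 and 3.

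Controls, under D.2, "will not have access to the education information or be instructed to change diet or lifestyle factors". The adherence telephone calls (D.2.7) concern the programme: "Designated health coaches will assess for adherence to the study intervention including dietary, stress management, and exercise recommendations".

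The primary outcome is PROMIS-29 (B.1, D.4.1), scheduled at all three visits (D.5). G.4 plans a linear mixed model with a random intercept and a group-by-visit test on all available data, but adds that "any participants who have baseline data only will be excluded from analysis".

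**The concern.** Excluded products and missed visits have their own categories. What is left under non-compliance is mainly failure to follow the diet, exercise, stress-management and supplement programme, and only one arm has that programme. The decision rests with investigators, no threshold is given, and the protocol describes no masking. Intervention men are also watched more closely, through daily app prompts, coaching calls and product counts.

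If a man leaves the study on this ground, the samples still to be sought from him serve the tertiary and exploratory outcomes. The primary outcome is not among them. If he leaves before Visit 2, he is replaced and drops out of the analysis set. At stake is whether the two arms are still the groups that randomisation formed when PROMIS-29 changes are compared. Scores that were never collected cannot be recovered by a later analysis plan.

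**Working it through.** **The plan's own figures.** No stated number underlies this point. The nearest is the attrition allowance in D.3.1: 48 enrolled for 40 evaluable, so 48 − 40 = 8 men lost for any reason, or 4 per arm if the loss is even. Allocation is 24 per arm (D.1). The protocol gives no effect size, SD or alpha, so everything below except the 24 per arm is an assumption.

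**What happens to a man withdrawn for non-compliance**

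| Time of withdrawal | Replaced? | PROMIS-29 in the primary analysis |
|---|---|---|
| Before Visit 2 | Yes | None; excluded as baseline-only |
| Between Visits 2 and 3 | No | Baseline and Week 5 kept; no Week 9 score planned |

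**Withdrawal before Visit 2, in points.** Let p be the share of intervention men removed. Suppose compliers gain δ and the removed men would have gained 0. The reported effect is δ and the as-randomised effect is (1 − p)δ. With δ = 3 and p = 4/24:

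- as-randomised: 3 × 20/24 = 2.5
- reported: 3.0
- excess: 0.5 points, or 0.5/2.5 = 20%

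This uses the arm's whole planned loss of 4 men for a single reason, and places all of it before any follow-up score. It is an upper-end illustration.

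**Withdrawal before Visit 2, when the programme has no effect.** Let g be the gap in mean change between compliers and non-compliers, in SD units. The bias is p × g. With 24 per arm the standard error is √(1/24 + 1/24) = 0.289 SD. The type I error at two-sided 0.05, by normal approximation, is 1 − Φ(1.96 − pg/0.289) + Φ(−1.96 − pg/0.289).

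| p | g = 0.5 SD: bias, type I error | g = 1.0 SD: bias, type I error |
|---|---|---|
| 10% | 0.05, 0.053 | 0.10, 0.064 |
| 20% | 0.10, 0.064 | 0.20, 0.107 |
| 30% | 0.15, 0.082 | 0.30, 0.180 |

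**Withdrawal between Visits 2 and 3.** Assume a within-person correlation ρ = 0.6, p = 20%, and a Week 9 gap of 0.5 SD. The random-intercept model predicts the missing Week 9 score from baseline and Week 5, with weight ρ/(1 + ρ) = 0.6/1.6 = 0.375 on each. The Week 9 bias is then p × (Week 9 gap − 0.375 × Week 5 gap):

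- no gap visible at Week 5: 0.2 × 0.5 = 0.10 SD
- half visible: 0.2 × (0.5 − 0.375 × 0.25) = 0.08 SD
- all visible: 0.2 × (0.5 − 0.375 × 0.5) = 0.06 SD

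Dropping these men entirely would give 0.10 SD. A simulation of the same model gave 0.102, 0.080 and 0.058. The mixed model lessens the bias to the extent that the gap already shows at Week 5, but it does not remove it.

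**The case against.** A reader might infer that the protocol removes poor adherers as a matter of course, leaving compliers to be compared with all controls and the randomised comparison broken. The documents do not support that.

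- The ground is tied to the participant's best interest and appears in a list for recording withdrawals. There is no adherence threshold.
- The stated response to poor adherence is coaching (D.7.5), and D.2.1 treats the diet as guidance with individual variation.
- Controls can withdraw, miss visits or take excluded products, and can be non-compliant in narrower ways, such as fasting, sampling or substance use. The replacement and baseline-only rules apply to both arms.
- Product counts first happen at the Week 5 visit, when PROMIS-29 is also collected. Earlier detection would rest on self-report. The mixed model keeps the Week 5 score.
- A bias in favour of the programme is not a given. It requires poor adherers to have worse changes. A stable difference in level would cancel, because the comparison is of changes.
- D.6 omits PROMIS-29 from post-withdrawal collection but does not forbid it, and a visit for final labs could include it.

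All of this stands, and it limits the likely size and certainty of the effect. It does not close the gap. The commitment after withdrawal still leaves out the primary outcome, and early leavers are still replaced and excluded. A separate analysis plan could settle analysis sets, but it could not supply scores that nobody collected.

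**Conclusion.** The point holds as a weakness in follow-up. Carried out as written, the plan can lose the primary outcome from poor adherers, mainly in the intervention arm: fully for withdrawals before Visit 2 and in part for later ones. How many men this would affect cannot be known from the protocol. On the assumptions shown, the upper-end case is 3.0 points reported against 2.5 as randomised. At 20% removal before Visit 2 under a true null, type I error would be 0.064 to 0.107 for gaps of 0.5 to 1.0 SD. With few or no such withdrawals the effect is negligible. The change is worth making because it is cheap and must be in place before data collection.

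**What to change.** Leave the clinical grounds for stopping as they are. In D.6, distinguish stopping the programme from leaving the study. Add PROMIS-29, with MYMOP, MSQ and the NUNM questionnaire, at Weeks 5 and 9 to the sentence on collection after withdrawal, for every randomised man who allows it. In G.4, replace the baseline-only exclusion with analysis of all randomised men in their assigned arm, including those who were replaced.

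Collection is the part that matters most. Keeping a baseline-only man in the model adds only his baseline, which does little to correct a gap that appears later. If every man supplies both follow-up scores, this selection bias is zero; men who decline remain missing. The cost is one amended paragraph in D.6, one sentence in G.4 and a few extra questionnaires, with no change in sample size.

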Study Title: Methylation Diet and Lifestyle (MDL) Study

PI: [name], ND, MPH and [name], ND

IRB #: RB100217

Approval Date: 2.9.18

Ver. 1.1

D.5 Participant Schedule

D.5.1 Overview

Individuals will be screened over the phone and at one in-person visit. Eligible participants who choose to enroll in the study will attend a total of 4 in-person visits. Participants will be randomized into either the intervention or control group after the screening visit. All study visits will be conducted at the Helfgott Research Institute in Portland, OR. Refer to Table 4 for an outline of the study visits.

Table 4: Study Procedures

	Phone Screening	Screening Visit	Study Visit 1 (Week 1)	Study Visit 2 (Week 5)	Study Visit 3 (Week 9)
Eligibility screening	X				
Consent for study participation		X			
Eligibility verification		X			
Demographic form		X			
W-9		X			
Anthropometrics/Vitals: height, weight, waist-hip ratio, heart rate, blood pressure, temperature, respiratory rate		X	X	X	X
Questionnaires: 
 • NUNM Multi-system Symptom/Adverse Event • MSQ • MYMOP • PROMIS-29 • Lifestyle Habits • VioScreen • Study specific FFQ 			X	X	X
Blood Draw, blood spot card and saliva sample			X	X	X

Protocol

Study Title: Methylation Diet and Lifestyle (MDL) Study

PI: [name], ND, MPH and [name], ND

IRB #: RB100217

Approval Date: 2.9.18

Ver. 1.1

DNA Methylation Pathway Profile - SNP Panel			X		
Infinium Methylation EPIC Index			X		X
Methylation Profile			X	X	X
Folate Vitamer Panel			X	X	X
Estimated Time to Complete	15 minutes	45 minutes	90 minutes	90 minutes	90 minutes

D.5.2. Recruitment

Recruitment will be conducted in the general community surrounding Portland, OR using flyers, online, newspaper, and electronic newsletters.

D.5.3. Telephone Screening

Potential participants will be screened over the phone prior to coming in for the first visit. A standardized telephone script will be used. The telephone screening call will take approximately 10-15 minutes. Participants who meet eligibility criteria over the phone will be scheduled for a screening visit. The consent form will be provided to participants prior to the screening visit via email; they will be instructed to review the form ahead of time but not to sign it until the screening visit where they can ask questions about the study. If an individual is eligible for the study, enrollment will happen on a rolling basis.

D.5.4. Screening Visit

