Once a participant is deemed eligible and provided signed consent, the study staff will determine randomization order using a random number generator (randomization.com). After enrollment, the study coordinator will select the next sequential envelope from the locked filing cabinet within the study site office. The study staff will write the current date and participant initials on the bottom right corner of the envelope and open the envelope and retrieve its contents. The envelope contents will show which cohort the participant is assigned to, with intervention or control. This will be assigned to the participant ID number and entered into REDCap.

D.5.7. Washout Period

Study participants assigned to the intervention group will be asked to refrain from taking any over-the-counter supplements, medications or herbal products, except short-term use (<1 week) and at least 1 week before scheduled study visits, alcohol, nicotine, marijuana or cannabinoids (including CBD products) or recreational drugs/substances for 3 weeks before the baseline visit. Written instructions will be provided.

D.5.8. Study Visits

There will be 3 in-person study visits for all participants during the 9-week study.

Baseline/Study Visit 1 (Week 1)

The following procedures, evaluation and/or assessments will be obtained at Study Visit 1:

- Height and weight
- Vital signs including heart rate, blood pressure, respiration rate and temperature

Protocol

Study Title: Methylation Diet and Lifestyle (MDL) Study

PI: [name], ND, MPH and [name], ND

IRB #: RB100217

Approval Date: 2.9.18

Ver. 1.1

- Questionnaires including Lifestyle Habits, PROMIS-29, MYMOP, MSQ, and NUNM Adverse Events, VioScreen
- Blood draw to collect 2 tubes of blood
- Finger stick to collect 5 drops of blood
- Saliva sample
- If in intervention group, will receive study supplements for first 4 weeks and instructions on how and when to take
- Case report form completed by study staff
- Waist-to-hip ratio will be calculated using the following methods:
 - Participant with stand up straight and breathe out. Use a tape measure to check the distance around the smallest part of the waist, just above the umbilicus. This is the waist circumference.
 - Measure the distance around the largest part of the hips — the widest part of the buttocks. This is the hip circumference.
 - Calculate the waist-to-hip ratio by dividing the waist circumference by the hip circumference.

Study Visit 2 (Week 5)

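### Section D.6 replaces men lost before Visit 2 although the 48 already allows for attrition, and replacement masks early leavers whom section G.4 drops from the primary analysis

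*Protocol*

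**What the plan says.** On size, protocol section D.1 states: "We will recruit forty-eight participants with 24 randomized to each study group". Section D.3.1 makes 48 a maximum and says what it contains: "We will enroll and randomize up to 48 people which will allow for 20% attrition", which is meant to leave "an evaluated sample size of 40 to allow for withdraws or dropouts".

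On withdrawal, section D.6 states: "If a participant withdraws before the second visit, they will be replaced". It goes on: "participants who withdraw between the second and third visits will not be replaced". The next sentence of D.6 promises an effort to obtain a last saliva sample and last laboratory tests from everyone, including early leavers. It does not mention questionnaires.

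On timing and assignment, section D.5.1 states: "Participants will be randomized into either the intervention or control group after the screening visit". Under D.5.6, once consent is signed, "the study coordinator will select the next sequential envelope from the locked filing cabinet". No separate procedure is given for a replacement.

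On analysis, section G.4 compares PROMIS-29 change between arms with a linear mixed model and leaves out anyone who has no data after baseline.

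**The concern.** A sample size that includes an attrition allowance is normally left to absorb the losses. Here one section sets a maximum with the allowance inside it, and another adds men whenever someone leaves before Week 5. The leavers are already randomised, so each replacement made after the 48th allocation exceeds the maximum.

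The second issue is what becomes of the leaver. A man who goes before Visit 2 contributes no later PROMIS-29 score, so G.4 removes him from the primary analysis. A new man then takes his place in the count, and the analysed number looks intact although randomised men have been lost. The primary outcome is self-reported and participants know their arm. If the men lost early differ between arms in number or in kind, the analysed arms are no longer the randomised ones, and a full-looking count makes that hard to see.

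**Working it through.** **Inputs from the protocol.** Maximum of 48, allowance of 20%, 40 evaluated (D.3.1); 24 per arm (D.1); replacement before Visit 2, which is Week 5 (D.6, Table 4); randomisation after screening (D.5.1, D.5.6); PROMIS-29 first collected at Visit 1, then at Visits 2 and 3 (Table 4); exclusion of men without data after baseline (G.4).

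**Not in the protocol, so assumed.** Early loss *e*; early loss by arm *dI* (intervention) and *dC* (control); the gap *k* in outcome between stayers and leavers, in SD; a two-sided 5% test.

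1. *Reproduce the stated size.* 40 × 1.20 = 48, so the 48 carries the allowance. (Dividing instead gives 40 / 0.80 = 50, and 48 × 0.80 = 38.4. Exactly 40 remain when the loss is 8/48 = 16.7%. This difference of two men is a separate, minor matter.)

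2. *Do early leavers count towards the 48?* Yes. Allocation follows screening, and for the intervention arm the 3-week washout and the baseline visit come after it. Anyone who leaves between allocation and Week 5 has been randomised.

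3. *Number randomised if replacement continues until 48 men reach Visit 2.* Formula: 48 / (1 − e).
   - e = 5%: 48 / 0.95 = 50.5
   - e = 10%: 48 / 0.90 = 53.3
   - e = 15%: 48 / 0.85 = 56.5
   - e = 20%: 48 / 0.80 = 60.0

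4. *What this does to the target of 40.* Hold total loss at 20% and vary how much of it is early.
   - None early: 48 randomised, 38.4 complete.
   - Half early: 53.3 randomised, 53.3 × 0.80 = 42.7 complete.
   - All early: 60 randomised, 60 × 0.80 = 48 complete.

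5. *Who remains in the primary analysis.* A man who leaves during the washout has no PROMIS-29 score. One who leaves between Visits 1 and 2 has a baseline score only. Unless a questionnaire is obtained later, which D.6 does not ask for, neither enters the G.4 analysis. This is so with or without replacement.

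6. *Possible selection.* Leaving out a fraction *d* of an arm moves its mean by d × k. With the same *k* in both arms, the contrast moves by (dI − dC) × k. For k between 0.25 and 1:
   - equal loss in both arms: 0
   - 20% against 10%: 0.10 × k = 0.025 to 0.10 SD
   - 30% against 10%: 0.20 × k = 0.05 to 0.20 SD
   - 5% against 15%: −0.025 to −0.10 SD, so the sign depends on which arm loses more

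7. *Effect on the error rate.* With 20 analysed per arm, the standard error of a simple two-group contrast is √(2/20) = 0.316 SD. A shift of 0.10 SD is 0.316 standard errors and raises the two-sided false-positive rate from 5% to about 6%. A shift of 0.20 SD is 0.632 standard errors and raises it to about 10%. This is a normal approximation, not the planned mixed model.

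**The case against.** The strongest reply is that the two provisions may cover different losses: replacement for those before Visit 2, the allowance for those between Visits 2 and 3. D.3.1 does not say which losses it means, so the claim that one loss is provided for twice is an inference. That much stands. It does not rescue the maximum, because D.3.1 limits the number randomised and the early leavers are among them.

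Three stronger readings are tempting, and the documents do not support them.

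- A reader might infer that replacement itself turns the intervention arm into men who tolerate the programme. D.6 does not say that a leaver's data are discarded or that he leaves the randomised set. The G.4 exclusion removes him, and it would do so if nobody were replaced.
- A reader might infer that a replacement takes the vacated place, so that staff know his arm before he enrols. The only procedure described is consent followed by the next envelope, and nothing exempts replacements from it. Under that procedure a vacated place need not be refilled in the same arm: if four men left one arm and new draws were independent and 1:1, the chance that all four refill it is 0.5⁴ = 6%. A small imbalance of this kind does little harm, and the 24 in D.1 is in any case a number randomised.
- A reader might infer that early loss falls mainly on the intervention arm. Only that arm has the washout, diet, supplements and daily tracking of the programme, so this is plausible. But no loss by arm is given, all entrants must be willing to follow the programme, intervention men get coaching calls, and wait-listed controls may also lose interest.

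An analysis plan that is not shown may define the analysis sets more fully. The number randomised, the replacement rule and the exclusion are, however, already fixed in the protocol.

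**Conclusion.** The concern holds in a limited form. D.6 and D.3.1 contradict each other once 48 men are randomised, and this needs no assumption. The excess depends on early loss: about 50 to 60 randomised for an assumed 5% to 20%.

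The statistical risk is conditional. G.4 removes early leavers from the primary analysis, D.6 seeks no questionnaire from them, and replacement hides the gap. If early loss or the kind of man lost differs by arm, the contrast is biased, by up to 0.20 SD in the scenarios tried. With equal loss and an equal stayer-leaver gap the bias is zero. The documents do not establish differential loss, so this is an avoidable exposure and not a demonstrated bias. Deleting the replacement sentence alone would not remove it, because its source is the exclusion and the missing follow-up.

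**What to change.** - In D.6, delete the replacement sentence. Alternatively, state that any extra men are additional randomisations by the next concealed envelope, never into the vacated arm, and restate the maximum number randomised in D.3.1 and D.1.
- State that every withdrawn man stays in the arm to which he was randomised.
- Extend the D.6 commitment on saliva and laboratory samples to PROMIS-29 at Week 5 and Week 9. This is the step that matters most for the primary outcome: retaining a man with only a baseline score adds no information on his change.
- Report the number lost before and after Visit 2, by arm.

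The cost is a short amendment and some effort to obtain questionnaires from leavers. Without replacement there may be slightly fewer evaluable men: 38.4 expected at 20% loss, 40 at 16.7%, and fewer if loss exceeds the allowance. If 40 are required at a true 20% loss, stating 50 randomised from the outset achieves that without replacement.
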